Historically, it has been used in viral diseases such as poliomyelitis, measles, mumps and influenza before vaccines became available.[28–32] A meta-analysis of 1703 patients with H₁N₁ influenza during the Spanish Flu of 1918 suggested that patients who received convalescent plasma had lower mortality.[33] Conversely, in a double blind, randomized, placebo-controlled trial, convalescent plasma was not found to be superior to placebo in patients infected with Influenza A.[34–36] Furthermore, 84 patients with Ebola virus disease who were transfused with convalescent plasma without known levels of neutralizing antibodies did not have a survival benefit.[37] Convalescent plasma was also studied during the previous coronavirus outbreak of SARS in 2002 -2004. In a retrospective study of 80 patients by Cheng et al, it was observed that patients who received convalescent plasma before day 14 of illness had better outcomes, defined as early hospital discharge, compared to patients who received it after day 14 of illness (15.6% vs 58.3%; P<0.001).[38] Considering the lack of efficacious treatments for COVID 19 and the epidemic situation with high mortality rate, US FDA has approved convalescent plasma for COVID-19 for clinical trials, expanded access and single patient emergency investigational new drugs (IND).[39]

Majority of the adverse effects associated with plasma transfusion are non-lethal; medically treatable adverse effects commonly associated with transfusion of plasma include TRALI; transfusion associated circulatory overload (TACO); allergic/anaphylactic reactions;

transfusion related transmission of infections (TTI); febrile non-hemolytic transfusion reactions (FNHTR); hemolytic transfusion reactions (HTR); and rarely RBC allo-immunization.[40] Another theoretical risk of using convalescent plasma includes antibody dependent enhancement of infection.[41]

Hypothesis and Objectives

We hypothesize that the use of convalescent plasma will improve the clinical outcomes in patients with moderate COVID-19 infection.

We designed this phase II, open label, randomized clinical trial with the primary objective to assess the safety and efficacy of the therapy in the second stage.

Efficacy Objective: To assess the efficacy of convalescent plasma to limit complications in COVID-19 patients.

Safety Objective: To evaluate the safety of treatment with anti SARS-CoV-2 plasma in patients with COVID-19.

Methods

Study Design

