4. Duration of respiratory support required
 - a. Duration of Invasive Mechanical Ventilation
 - b. Duration of Non-Invasive

5. Radiological improvement
6. Adverse events (AE) associated with transfusion
7. To measure the change in RNA levels (Ct values) of SARS-CoV-2 from RT-PCR [Time Frame: Days 0, 1, 3, and 7 after transfusion]
8. Correlation between Viral neutralization titer and Elisa antibody Assay
9. Correlation between titers in donor plasma and IgG titer on transfusion
10. Levels of bio-markers pre and post transfusion
11. Need of Vasopressor use
12. Pre and post transfusion antibody titers

Other Exploratory Endpoints

1. Cumulative incidence of serious adverse events during the study period: transfusion reaction (fever, rash), transfusion related acute lung injury (TRALI), transfusion associated circulatory overload (TACO), transfusion related infection
2. Rates and duration of SARS-CoV-2 PCR positivity (RT-PCR) from days 0 and if further available.

Analysis Plan

Baseline data about the demography, clinical presentations, ongoing medical therapy, and clinical history of participants in both arms will be collected and compared. Response to convalescent plasma will be coded as a binary outcome – based on whether the composite primary end point is met or not. Adverse events associated with infusion of convalescent plasma will also be descriptively summarized and compared with the adverse events experienced by participants receiving standard of care.

The objective response rate, defined as the proportion of participants successfully meeting the primary end points, will also be reported, along with a two-sided 95% confidence interval calculated using the Clopper-Pearson method.[45] This will be compared between the intervention and control groups.

Participants who drop off from the treatment arm prior to evaluation of post-intervention response will be considered as non-responders, regardless of the discontinuation reasons, and will be included in the intention to treat analysis. Comparison between group response rates will be analyzed and reported.

Study Procedures:

	Screen	Baseline	Intervention (Convalescent Plasma infusion)	Follow-up				
Day	-1 to 0	0	0	1	3	7	14	28
Pre-Intervention Screening								
Eligibility screening and Informed Consent	x							

Demographic and Medical history	x							
SARS-CoV-2 RT-PCR test for eligibility	x							
Pregnancy test	x							
ABO	x							
Study Intervention								
Symptom checking	x	x	x	x	x	x	x	x

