Indicative list of supplies/logistics necessary to conduct this study.

SI No	Item name
1	Anti-A
2	Anti-B
3	Anti-D
4	Antibody screen
5	Complete blood count
6	Serology (HIV, HBV, HCV, Syphilis & malaria)
7	NAT test (HIV, HBV & HCV)
8	Rapid IgG and IgM tests for COVID-19
9	IgM ELISA
10	IgG ELISA
11	Plasmapheresis disposable kit
12	Transfer bags
13	EDTA vials
14	Plain vials
15	20ml syringes
16	PPE kits
17	ELISA reader and washer
18	BBR-cum-freezer
19	Biosafety cabinet type 2
20	Donor Transport
21	Staff (technician / research associate)

Safety Assessments and Reporting

Definition of adverse event

An Adverse Event/Experience [AE] is any untoward medical occurrence in a participant undergoing TPE, is one which does not necessarily have a causal relationship with the TPE procedure. It can be any unfavorable and unintended sign, symptom, or disease, which is temporally associated with the use of convalescent plasma, whether or not considered to be causally related to convalescent plasma.

A Serious Adverse Event [SAE] is any untoward medical occurrence, at any point during convalescent plasma, results in:

- Death
- A life-threatening condition. This means any event in which the participant is at risk of death; it does not refer to a condition, which, with increasing severity, may result in death.
- Significant disability

Other medically significant outcomes, which may not result in any of the above, but may jeopardize the well-being of the participant, requiring greater degrees of medical or surgical interventions to prevent one of the outcomes listed above.

Data Management

Data Management Responsibilities

The Investigators will be responsible for assuring completeness, accuracy and timely collection of data. Case Record Forms (CRFs) should support the data entered in the electronic data capture system. They will be signed and dated by the person filling out the forms, and the investigator reviewing the same. Data will be reviewed by the Investigator and co-signed. Data management will be undertaken by ICMR-National Institute of Epidemiology.

Data Capture Methods

Paper CRFs will be used to collect data. The data will then be entered on an electronic system. A data entry system with electronic tracking, password restricted access, audit trail, with time and date stamps on data entry and edits, will be developed.

Types of Data

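### The only planned safety comparison between arms restricts plasma-arm events to those associated with infusion but leaves control-arm events unrestricted, so it does not compare like with like

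*Protocol*

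**What the plan says.** The protocol plans one comparison of adverse events between arms, in the Analysis Plan: "Adverse events associated with infusion of convalescent plasma will also be descriptively summarized and compared with the adverse events experienced by participants" on standard care. The plasma side is "Adverse events associated with infusion of convalescent plasma"; the control side is "the adverse events experienced by participants receiving standard of care". The first phrase carries a qualifier and the second carries none.

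The narrow scope recurs in the endpoint lists. Secondary outcome 6 is "Adverse events (AE) associated with transfusion". The first exploratory endpoint opens with "Cumulative incidence of serious adverse events during the study period: transfusion reaction (fever, rash" and goes on to lung injury, circulatory overload and infection, each tied to transfusion.

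The aim is wider. Under Hypothesis and Objectives, safety is part of the primary objective, and the safety objective is "To evaluate the safety of treatment with anti SARS-CoV-2 plasma in patients with COVID-19". The second Safety Assessments and Reporting section, under Definition of adverse event, includes events "temporally associated with the use of convalescent plasma, whether or not considered to be causally related to convalescent plasma". The Study Procedures table schedules adverse event monitoring on Days 0, 1, 3, 7, 14 and 28 without separating the arms.

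**The concern.** These are hospitalised patients with background morbidity. The Sample Size section assumes 18% mortality under standard care, and the introduction lists sepsis, respiratory failure, ARDS, cardiac injury and acute kidney injury as common complications. If such events count in controls, but in plasma patients only when linked to the infusion, the two columns of the safety table measure different things.

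A plasma arm with the same background illness, plus some harm from transfusion, could then look safer than control. The fault lies in the analysis sentence, so repairing the adverse event definitions alone would not remove it. The documents fix this comparison; it is not a detail left open for a later plan.

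**Working it through.** **Inputs from the protocol.** 226 patients per arm; proportions 0.18 and 0.09; two-sided 0.05; power 0.80; pooled-variance Z test (Sample Size). The protocol gives no adverse event rates.

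**The plan's own figure.** The mean proportion is (0.18 + 0.09)/2 = 0.135.

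n = [1.960·√(2 × 0.135 × 0.865) + 0.8416·√(0.18 × 0.82 + 0.09 × 0.91)]² / 0.09² = (0.947 + 0.403)² / 0.0081 ≈ 225.1, rounded up to 226.

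The stated size reproduces (power at 226 is 80.2%) and is not affected by this point.

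**Set-up for the safety comparison.** Let b be the risk of at least one background event, equal in both arms, and i an independent infusion-associated risk in the plasma arm. Assume first that the definitions cover controls and that the restriction is read narrowly.

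- All events in both arms: difference = [1 − (1 − b)(1 − i)] − b = i(1 − b).
- As written: difference = i − b.
- Distortion = (i − b) − i(1 − b) = −b(1 − i), negative whenever b > 0 and i < 1.

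**Illustration.** b = 0.18 is the protocol's mortality figure, used only as a floor for background events; i = 0.05 is an assumption.

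| Comparison | Plasma | Control | Difference |
|---|---|---|---|
| All events in both arms | 226 × 0.221 ≈ 50 | 226 × 0.18 ≈ 41 | +4.1 points |
| As written, narrow reading | 226 × 0.05 ≈ 11 | 41 | −13.0 points |

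The distortion is −0.18 × 0.95 = −17.1 points, and the sign reverses. Over assumed ranges b = 0.09 to 0.50 and i = 0 to 0.10, the distortion runs from −8.1 points (b = 0.09, i = 0.10) to −50.0 points (b = 0.50, i = 0).

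**Sensitivity to the reading.** Suppose a plasma patient's background event is counted as associated with probability f. The distortion becomes −b(1 − f)(1 − i). In the same example:

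- f = 0 (narrow): −17.1 points.
- f = 0.5: −0.18 × 0.5 × 0.95 = −8.6 points.
- f = 1 (temporal link, whole follow-up): 0.

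The distortion cancels the true +4.1 points when (1 − f) × 17.1 = 4.1, that is at f ≈ 0.76.

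**Sensitivity to the definitions.** As they stand, the adverse event and serious adverse event definitions are tied to TPE or to plasma. If no control event were counted for that reason, the narrow reading would give 5.0 − 0 = +5.0 points and the broad reading 22.1 − 0 = +22.1 points, against +4.1 like for like. Both err against plasma. The direction in favour of plasma therefore holds only after the definitions are extended to controls.

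**The case against.** The strongest defence is that the link is temporal. The first Safety Assessments and Reporting section describes recipient reactions by their timing relative to administration, and the later definition does the same and disregards causality. Read that way over the whole follow-up, the plasma side approaches all events and the distortion disappears. This stands as a possible reading. However, the Analysis Plan sets no window, and secondary outcome 6 and the list of transfusion complications point to the narrow reading.

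Second, death and progression to severe ARDS are compared between arms in the primary outcome without any attribution. Vasopressor need, duration of respiratory support and hospital stay are also listed without it. This stands too and limits what is exposed.

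Third, the comparison is descriptive, and tabulation detail may sit in an analysis plan not shown. No error rate or power is affected. But the protocol does state what is compared with what, and that statement is uneven.

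Several stronger inferences are tempting and not supported:

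- **An unblinded clinician decides which plasma-arm events count.** The trial is open label, but no section sets up a causality assessment or names an assessor.
- **The Analysis Plan flatly contradicts the adverse event definition.** It does so only if association with infusion is read as causal.
- **Serious respiratory harm from plasma would vanish from view.** Severe ARDS and death remain in the primary outcome.
- **The artefact can be stated in standard errors.** That would rest on event rates the protocol does not give, for a comparison with no planned test.

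**Conclusion.** The point holds as a badly fixed comparison. On its wording, the only planned adverse event comparison sets a restricted set of events against an unrestricted one, with no criterion for the restriction and no all-event comparison elsewhere, on a matter that is part of the primary objective.

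Its direction and size are conditional. It favours plasma if the restriction is read narrowly and once the definitions cover control patients. Its size is then b(1 − i), or 17.1 points in the illustration; that figure rests on an assumed i, equal and independent background risk, and a mortality rate used as a floor. A broader reading reduces it towards zero, and unrepaired definitions could reverse it. In practice the exposure is mainly adverse and serious adverse events other than death and severe ARDS, for example kidney or cardiac injury. The sentence should be corrected; the sample size and primary analysis are untouched.

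**What to change.** Replace the sentence in the Analysis Plan with wording to this effect:

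*All adverse events and all serious adverse events, regardless of attribution and under one definition that applies to both arms, will be summarised and compared between arms from randomisation to Day 28. Events associated with infusion, by a stated criterion and time window, will be listed separately for transfused patients and not compared with the control arm.*

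Align secondary outcome 6 with this, and extend the adverse event and serious adverse event definitions to control patients at the same time, because the comparison depends on them.

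The cost is a few sentences. The Study Procedures table already schedules the monitoring to Day 28 without separating arms. The downside is slightly longer tables and a plasma-arm event rate that looks less favourable.

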Multi-center, two-arm, prospective, Phase II, open label, randomized controlled trial.

Study Population

Hospitalized COVID-19 patients fulfilling the inclusion and exclusion criteria, and admitted for care at COVID-19 management facilities in India will be eligible for inclusion in the trial.

Inclusion Criteria

1. Patients admitted with RT-PCR confirmed COVID-19 illness.
2. Age > 18 years
3. Written informed consent
4. Has any of the two
 - a. PaO₂/ FiO₂ <300
 - b. Respiratory Rate > 24/min and SaO₂ ≤ 93% on room air

Exclusion criteria

1. Pregnant women
2. Breastfeeding women

3. Known hypersensitivity to blood products
4. Receipt of Pooled Immunoglobulin in last 30 days
5. Critically ill patients:
 - a. P/F ratio <200 (moderate - severe ARDS)
 - b. Shock (Requiring Vasopressor to maintain a MAP \geq 65mmHg or MAP below 65)
6. Participating in any other clinical trial
7. Clinical status precluding infusion of blood products

Assessment of donor for eligibility

COVID-19 convalescent plasma will be collected from recovered individuals if they are eligible to donate blood. Considerations for assessment of donor for eligibility are outlined in the section on convalescent plasma.

Sample Size

For sample size calculation, we considered that given the standard of care, 18% of patients would succumb to COVID-19 infections.[5] We considered a relative effectiveness of 50% for sample size calculations. We calculated sample size using the PASS v11.0 software.[42]

Group sample sizes of 226 in the intervention group and 226 in the control group achieve 80% power to detect an absolute difference of -0.09 between the group proportions. The proportion of participants meeting the primary outcome in group one (the treatment group) is assumed to be 0.18 under the null hypothesis and 0.09 under the alternative hypothesis. The proportion of participants in group two (the control group) who meet the primary outcome is assumed to be 0.18 based on current evidence.[5] The test statistic used is the two-sided Z test with pooled variance. The significance level of the test was targeted at 0.05, with a power of 0.8.

Primary Outcomes

The primary outcome is a composite measure of the avoidance of -

1. Progression to severe ARDS (P/F ratio <100) and
2. All-cause Mortality at 28 days

Secondary Outcomes

1. Time to symptom resolution
 - a. Fever
 - b. Shortness of Breath
 - c. Fatigue
2. Hospital length of stay
3. Change in SOFA pre and post transfusion

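### The non-responder rule for drop-outs is written for the plasma arm only; unless control drop-outs are also scored as failures, the primary comparison is biased against plasma, and 226 per arm has no drop-out allowance

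*Protocol*

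**What the plan says.** The Analysis Plan of the protocol codes the composite primary endpoint as a binary response, reports a response rate for it, and compares that rate between the intervention and control groups. Its one rule for participants who leave early is: "Participants who drop off from the treatment arm prior to evaluation of post-intervention response will be considered as non-responders, regardless of the discontinuation reasons". These participants stay in the intention-to-treat analysis. Nothing is said about participants who leave the control arm.

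The Sample Size section shows which arm is meant. The primary-outcome proportion "in group one (the treatment group) is assumed to be 0.18 under the null hypothesis", and group two is called the control group. For a planned reduction of 9 percentage points, the same section states: "Group sample sizes of 226 in the intervention group and 226 in the control group achieve 80% power". It mentions no drop-out rate and no inflation for drop-out.

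**The concern.** A rule that turns drop-outs into failures is a legitimate choice when both arms are scored alike. Written for one arm, it adds failures to that arm alone, and the between-arm difference then partly measures how many people left the plasma arm. Keeping them in the intention-to-treat set does not repair this if the two arms are scored by different rules. The trial is open label, so leaving may itself depend on allocation.

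Two things are at stake. A real benefit of the planned size could be missed, and a plasma arm that does no harm could be reported as significantly worse.

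**Working it through.** **Inputs from Sample Size.** Failure rates: the treatment proportion is "assumed to be 0.18 under the null hypothesis and 0.09 under the alternative hypothesis"; the control proportion "who meet the primary outcome is assumed to be 0.18 based on current evidence". Test: "The test statistic used is the two-sided Z test with pooled variance". Error rates: "The significance level of the test was targeted at 0.05, with a power of 0.8". I read 0.18 and 0.09 as failure rates (severe ARDS or death), since the section derives them from mortality. A non-responder is then a failure.

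**The plan's own figure.** With mean rate 0.135,

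n = [1.96·√(2·0.135·0.865) + 0.8416·√(0.09·0.91 + 0.18·0.82)]² / 0.09² = 225.1, so 226 per arm.

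At 226 per arm the normal-approximation power is 80.2%; exact binomial enumeration of the same test gives 81.1%. The stated figure therefore reproduces, with no allowance for drop-out in it.

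**Assumptions not in the protocol.** Drop-out rate d of 0% to 10%, equal in both arms and unrelated to outcome. For the literal one-arm reading, control drop-outs are excluded.

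**Bias.** If the true plasma failure rate is p, the scored rate is p(1−d) + d = p + (1−p)d. The excess is (1−p)d: 0.91d when p = 0.09 and 0.82d when p = 0.18. The control rate stays at 0.18. The planned difference disappears when 0.91d = 0.09, that is at d = 9.9%.

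**One-arm rule**, exact enumeration, plasma n = 226, control n = 226(1−d) rounded:

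| d | Scored plasma rate if true rate is 0.09 | Difference from 0.18 | Power for benefit | Scored plasma rate if no effect | Chance of significant harm |
|---|---|---|---|---|---|
| 0% | 0.0900 | 0.0900 | 81% | 0.1800 | 2.5% |
| 2% | 0.1082 | 0.0718 | 59% | 0.1964 | 6% |
| 5% | 0.1355 | 0.0445 | 25% | 0.2210 | 19% |
| 10% | 0.1810 | −0.0010 | 2% | 0.2620 | 53% |

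The normal approximation agrees (58.1%, 24.9% and 2.3% power at 2%, 5% and 10%). Excluding control drop-outs is not what drives the result: with 5% drop-out in plasma and none in control, exact power is 26%.

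**Comparison rules** at 226 randomised per arm, exact:

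- Non-responder in both arms: power 67% at 5% and 55% at 10%. There is no bias under no effect, and the planned difference shrinks only to 0.09(1−d), for example 0.0855 at 5%.
- Available cases in both arms: power 79% at 5% and 76% at 10%.

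**Splitting the loss at 5%.** From 81% to 67% (14 points) is the price of non-responder scoring with no allowance in the sample size. From 67% to 25% (42 points) is due to the asymmetry.

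**The case against.** The strongest reply is that the asymmetry is inferred from silence. The protocol does not say that control drop-outs are excluded or counted as successes, and an analysis plan not shown here may apply the same rule to them. The section's wording is also loose: it describes the binary outcome as response to plasma while comparing it across both arms, so naming one arm may be careless drafting. This stands to the extent that the bias must be stated conditionally. It does not remove the point, because the protocol does fix a rule and limits it to one arm. A plan that followed the sentence would score the arms differently, and one that did not would depart from it.

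Stronger readings that a reader might infer, and that the documents do not support:

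- That 80% power cannot be reached. It reproduces with complete data, and every loss above rests on an assumed drop-out rate.
- That the rule overrides known day-28 outcomes. It reaches only those who leave before their response is evaluated; the clause about reasons concerns why they left, not whether the outcome is known.
- That the bias always runs against plasma at 0.91 times drop-out. That factor needs the 9% alternative and drop-out unrelated to outcome. If plasma drop-outs would mostly have failed anyway, scoring them as failures adds little error in that arm. If control drop-outs are also failures and are more frequent, the bias favours plasma.
- That the whole power loss comes from the asymmetry. At 5%, about a quarter of it (14 of 56 points) does not.

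It is also fair to say that, on the literal reading, the error is conservative for a claim of benefit. It is not conservative for a finding of harm.

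**Conclusion.** The point holds in conditional form. The drop-out rule names the plasma arm alone and feeds the between-arm comparison. Applied literally, with control drop-outs not scored as failures, it biases the comparison against plasma by (1−p) times the plasma drop-out rate when drop-out is unrelated to outcome. Even 2% drop-out, if equal in both arms and excluded in control, would take power from 81% to 59% and raise the false-harm probability from 2.5% to 6%; at 5% the figures are 25% and 19%. The protocol states no drop-out rate, so these show sensitivity and are not forecasts. If the same rule applies in both arms with equal drop-out, the bias under no effect vanishes, but power at 226 per arm still falls below 80% because the sample size carries no allowance.

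**What to change.** Replace the sentence in the Analysis Plan with one that covers both arms:

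- All randomised participants are analysed in the arm to which they were allocated.
- Observed day-28 vital status and severe-ARDS status are used wherever known.
- One identical rule applies in both arms to outcomes that are truly missing, with a sensitivity analysis under an alternative rule. Which rule is chosen can be left to the statistical analysis plan, provided that it is the same in both arms.

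In Sample Size, state that 226 per arm contains no drop-out allowance and that 80% power therefore assumes essentially complete outcome data. Give the power under the chosen rule over a range of assumed drop-out.

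The cost is one changed paragraph and a lower stated power. The drop is slight with available cases (79% at 5%, 76% at 10%) and larger with non-responder scoring in both arms (67% and 55%). The schedule already has a day-28 contact, so little new data collection is needed beyond establishing status for those who leave.

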Randomization	x							
Convalescent Plasma Infusion			x					
Vital signs	x	x	xxxxx ¹	x	x	x	x	x
Physical examination	x		x	x		x		x
Concomitant medications		x	x					
Adverse event monitoring			x	x	x	x	x	x
Lab Investigations								
CBC and CMP		x		x		x	x	
SARS-CoV-2 RT-PCR		x			x	x	x	
SARS-CoV-2 antibody		x		x	x	x	x	
Blood for testing and archiving		x		x	x	x	x	
Imaging		x		x				x
Others	As clinically indicated							

1 Vital signs need to be tested immediately prior to infusion, within 15 minutes after initiation of infusion, at the completion of infusion and within 1 hour of end of infusion

Convalescent plasma:

Eligibility of Donor

Potential donors will include the following[39]:

- Prior diagnosis of COVID-19 documented by a laboratory test and
- Complete resolution of symptoms and at least one negative lab test for COVID-19 at least 28 days prior to donation (as per NBTC guidelines after COVID -19 pandemic for donor selection). If plasma is collected prior to 28 days after full recovery from illness, then confirmation of the resolution of the infection should be obtained through demonstration of two non-reactive Nucleic Acid Tests (NAT) for SARS-CoV-2 performed at an interval of at least 24 hours on nasopharyngeal swabs.
- These individuals will be contacted telephonically and explained the details of the study and their extent of participation. They will be encouraged to visit the main blood bank for further evaluation towards eligibility for blood donation. If requested, they will be provided transport for the same.

Recruitment of Donor

At the time of discharge, all recovered COVID-19 patients will be counselled. They will be motivated towards donation of convalescent plasma after 28 days of symptom free period and its probable beneficial effects in the management of COVID-19 patients. Such patients will be briefed in detail regarding their extent of participation in the study. Later on, these individuals will be contacted telephonically on Post discharge Day 25. They will be encouraged to visit the Blood Bank for further evaluation towards eligibility for blood donation. If need arises, the participant will be provided conveyance for facilitating transport.

Donor eligibility criteria

The following eligibility criteria will be applied towards potential donors:

1. Only males and nulliparous female donors of weight > 55 kgs will be included.

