For infusion of plasma existing SOP of the wards w.r.t transfusion of FFP should be followed with special care to monitor these patients during and post-24 hours of transfusion. All such transfusions have to be done using blood transfusion sets. The clinician will send a request for plasma component specifically mentioning the diagnosis and that convalescent plasma is required. An ABO compatible plasma bag of approx. 200ml will be issued maintaining all the blood bank records after thawing at 37 degree Celsius. the first plasma transfusion may be followed by one or two additional doses of 200 mL at 24 hours interval according to disease severity and tolerance of the infusions. The second plasma unit will preferably be from a different donor depending on the availability of another ABO compatible plasma unit or else plasma unit from the same donor will be issued.

Safety Assessments and Reporting

Definition of adverse events[45,46]

- Donor-related adverse events: They were divided into local reactions and systemic reactions. AEs were classified according to severity into mild, moderate, and severe and according to etiology in a donor into hypotensive reactions, citrate reactions, hematomas, loss of consciousness, seizures, and allergy.
- Kit/ Equipment-related adverse events: These are secondary to improper disposable sets. These are hemolysis, thrombus formation, air embolism, leakage, infection, improper mounting of the kits etc.
- Recipient related adverse events: A transfusion-related adverse reaction is a response or effect in a patient temporally associated with the administration of blood or blood components. Majority of the non-lethal and medically treatable adverse effects commonly associated with transfusion of plasma include transfusion related acute lung injury (TRALI); transfusion associated circulatory overload (TACO); allergic/anaphylactic reactions; transfusion related transmission of infections (TTI); febrile non-hemolytic transfusion reactions (FNHTR); hemolytic transfusion reactions (HTR); and rarely RBC allo-immunization

Details of Standard of care

The Ministry of Health and Welfare has issued detailed guidelines for the management of sCOVID-19 based on varying grades of severity.[47] For the management of ARDS or sepsis, the respective guidelines issued by ARDSNet and Surviving Sepsis campaign will be followed. Other institutional protocols for supportive management will be implemented.

Logistics of Investigational Products

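### The AE and SAE definitions name a procedure outside this trial and are tied to plasma use, which contradicts the planned two-arm safety comparison, the SAE endpoint's window and monitoring to day 28

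*Protocol*

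**What the plan says.** The protocol has two sections headed Safety Assessments and Reporting. The second, under Definition of adverse event, contains the general definitions:

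- **AE, population:** "any untoward medical occurrence in a participant undergoing TPE, is one which does not necessarily have a causal relationship with the TPE procedure". The available text neither expands nor describes TPE. The two arms are convalescent plasma infusion and standard of care.
- **AE, exposure:** the following sentence describes an unfavourable sign, symptom or disease "which is temporally associated with the use of convalescent plasma, whether or not considered to be causally related to convalescent plasma".
- **SAE, window:** "any untoward medical occurrence, at any point during convalescent plasma, results in" death, a life-threatening condition or significant disability, with a further clause for other events that need more intervention.

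Other sections work to a different scheme:

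- **Analysis Plan:** AEs linked to the plasma infusion are to be summarised descriptively and then "compared with the adverse events experienced by participants receiving standard of care".
- **Other Exploratory Endpoints:** the first item begins "Cumulative incidence of serious adverse events during the study period: transfusion reaction (fever, rash" and goes on to lung injury, circulatory overload and infection related to transfusion.
- **Study Procedures:** the row "Adverse event monitoring" is marked for the infusion day and days 1, 3, 7, 14 and 28, and names no arm.
- **Hypothesis and Objectives:** safety is part of the primary objective.

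**The concern.** A comparison of harms between randomised arms needs one rule for what counts as an event and one period over which it counts, both independent of the treatment received. Here the general definitions depend on exposure. A control participant receives neither TPE nor plasma, so no general definition in the protocol covers that participant's events, although the Analysis Plan expects to report them. A plasma recipient with a serious event in week two falls outside the SAE wording but inside the SAE endpoint's period.

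The trial is open label, so staff know each patient's arm when deciding whether an event fits the definition. Non-fatal harms are the most exposed. The protocol's background lists sepsis, cardiac injury and acute kidney injury among common complications, and no listed outcome names them. A statistical analysis plan cannot repair this afterwards, because events not recorded at the site cannot be recovered.

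**Working it through.** **1. The plan's own figure.** The only computed design figure is the sample size. It is used below only as a denominator. Inputs from the Sample Size section: p₁ = 0.18, p₂ = 0.09, two-sided α = 0.05, power 0.80, pooled-variance Z test.

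n = [1.960·√(2·0.135·0.865) + 0.842·√(0.18·0.82 + 0.09·0.91)]² / 0.09² ≈ 225.1, rounded up to 226 per arm. Power at 226 is 0.8015. The figure reproduces.

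**2. The passages side by side.**

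| Question | Definition of adverse event | Analysis Plan, endpoints, schedule |
|---|---|---|
| Who can have an AE? | A participant undergoing TPE (neither arm), with a link in time to plasma use | Participants in both arms |
| When can an SAE occur? | While on plasma | Throughout the study |
| How long are AEs followed? | No end stated | To day 28 |
| What is compared? | – | Infusion-associated AEs (plasma) against all AEs (control) |

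The first two rows are contradictions. The last is an asymmetry within the Analysis Plan sentence itself.

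**3. What each reading would record.** The protocol gives no AE or SAE rate, so the risk is an assumption. Suppose the true all-cause risk is 10% in both arms: 0.10 × 226 = 22.6, or 23 events each.

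- *TPE wording taken as binding:* nobody qualifies, so 0 versus 0.
- *TPE ignored, plasma link enforced:* controls 0; plasma at most 23, and fewer SAEs if only those during plasma treatment count.
- *Analysis Plan sentence taken literally:* controls 23; plasma anywhere from 0 to 23, depending on how many events are judged associated with infusion.
- *One all-cause definition for both arms:* 23 versus 23.

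**4. Size across assumed risks.** Each row takes the extreme in which one arm's events are all counted and the other's are not. Fisher's exact p is shown only to gauge the size; the protocol states no test for AEs.

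| Assumed risk, both arms | Recorded, one arm v other | Fisher p | Same rule in both arms |
|---|---|---|---|
| 2% | 5 v 0 | 0.061 | 5 v 5, p = 1.0 |
| 5% | 11 v 0 | 0.0009 | 11 v 11, p = 1.0 |
| 10% | 23 v 0 | 1.3 × 10⁻⁷ | 23 v 23, p = 1.0 |

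The arms are equal in size, so the two-sided p is the same whichever arm goes uncounted. These are bounds, not predictions. They show that the definition alone could create a large apparent difference, in either direction, where none exists.

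**The case against.** The strongest reply is that this is loose drafting and that the rest of the protocol shows the intent. The Analysis Plan foresees AEs in standard-of-care participants, the monitoring row is not limited to one arm, and the SAE endpoint runs over the study period. The AE sentence about plasma can be read as illustrative, and its link in time has no stated end, so only the SAE phrase raises a window problem. The between-arm comparison is descriptive, and the secondary outcome of transfusion-associated AEs can be measured in the plasma arm. All of this stands as evidence of intent. It does not tell a site which of two incompatible rules to follow.

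Several stronger readings are tempting, but the documents do not support them:

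- *Control patients cannot have events, so the comparison is invalid.* This lets one section override the others. The protocol contradicts itself; it does not set a rule of zero control events. Read literally, the TPE sentence excludes plasma recipients too.
- *The comparison must show excess harm from plasma.* The Analysis Plan sentence can push the other way, as step 3 shows.
- *About 41 control deaths (0.18 × 226 = 40.7) would be lost.* Death from any cause by day 28 is in the primary outcome for both arms, as is severe ARDS. Delayed harm from antibody-dependent enhancement that led to either would also be seen there.
- *Listing fever and rash breaks the seriousness criteria.* The parenthesis describes a type of reaction, and the SAE list has a clause that could admit serious cases.
- *The recipient definition is at fault.* The first safety section says "A transfusion-related adverse reaction is a response or effect in a patient temporally associated with the administration of blood or blood components". A transfusion reaction properly applies only to those transfused.

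**Conclusion.** The definitions are wrong as written and should be corrected before events are recorded under them. They name a procedure outside the trial, tie AEs to plasma use and SAEs to the time of plasma treatment, and so contradict the protocol's own comparison, endpoint window and schedule. If they are applied literally, ascertainment of non-fatal AEs and SAEs differs by arm, late SAEs in the plasma arm may go uncounted, and the comparison is biased in an unpredictable direction.

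The size cannot be fixed from the documents, since no AE rate is given. With equal assumed risks of 2% to 10%, the spurious difference could reach 5 to 23 events per 226. This assumes complete non-recording in one arm; sites following the Analysis Plan's evident intent would produce less. Mortality to day 28 and severe ARDS are unaffected, so the safety part of the primary objective is weakened rather than unanswerable.

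**What to change.** Reconcile the second safety section, the Analysis Plan, the exploratory SAE endpoint and the Study Procedures table:

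1. Delete the references to TPE.
2. Define an AE as every unfavourable medical event in a randomised participant of either arm, whether or not related to treatment, from randomisation to day 28. Define SAEs over the same people and period, keeping the seriousness criteria.
3. In the Analysis Plan, compare all-cause AEs and all-cause SAEs between arms.
4. Report transfusion reactions separately and descriptively in the plasma arm.
5. State that the AE monitoring row applies to both arms. As the table reads, randomisation sits in the column for days -1 to 0 and AE monitoring starts at the infusion column, so the row should start at randomisation.

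The cost is protocol and CRF wording, plus AE recording in controls at visits already scheduled. Sample size and the efficacy analysis do not change.
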